3.3. Strata and Covariates

Subjects will be randomly assigned to treatment groups via the interactive web response system (IWRS) in a 1:1:1:1 ratio using a stratified randomization schedule. Stratification will be based on the following variables:

- Use of concurrent immunomodulatory drugs at baseline (Y/N: conventional synthetic disease modifying antirheumatic drugs (csDMARD[s]) or corticosteroids)
- Hematologic + biological component scores of the ESSDAI obtained at screening (combined score of <2 or ≥ 2)

Only systemic use of csDMARDs (route of administration oral, subcutaneous, intramuscular, or intravenous) is considered for the stratification. If there are discrepancies in stratification factor values between the IWRS and the clinical database, the values recorded in the clinical database will be used for analyses. If it is impossible to derive the stratification factor from the clinical database due to missing values, data from IWRS will be used.

Efficacy endpoints will be evaluated using stratification factors as covariates or stratification variables for analyses, as specified in Section 6.

For efficacy endpoints, the baseline value of the efficacy variable(s) will be included as a covariate in the efficacy analysis model.

3.4. Examination of Subject Subgroups

The primary and secondary efficacy endpoints will be examined using the following baseline characteristics and randomization stratification variables:

- Age (< 50 years and ≥ 50 years)
- Diagnosis of autoimmune disease (Yes and No)
- Diagnosis of SLE (Yes, No)
- Diagnosis of RA (Yes, No)
- Duration of the disease (<5 years, ≥ 5 years)
- Use of concurrent immunomodulatory drugs (csDMARD or corticosteroids) at baseline (systemic use of these medications at Day1 – Yes and No)
- Hematological + biological component scores of the ESSDAI obtained at screening (combined score of <2 and ≥ 2).
- ESSDAI at Baseline (<14 and ≥ 14)

3.5. Multiple Comparisons

All endpoint tests will be done at the significance level of 0.05 with no multiplicity adjustment in this proof-of-concept study.

3.6. Missing Data and Outliers

3.6.1. Missing Data

In general, missing data will not be imputed unless methods for handling missing data are specified. Exceptions are presented in this document.

For missing last dosing date of study drug, imputation rules are described in Section 4.2.1. The handling of missing or incomplete dates for determining treatment emergent AE status is described in Section 7.1.5.2. The handling of missing date for prior and concomitant medications is described in Section 7.4. Imputation rules adopted in the efficacy analyses are specified in Section 6.

3.6.2. Outliers

Outliers will be identified during the data management and data analysis process, but no sensitivity analyses will be conducted. All data will be included in the data analysis.

3.7. Data Handling Conventions and Transformations

In general, age (in years) on the date of the first dose of study drug will be used for analyses and presentation in listings. If an enrolled subject was not dosed with any study drug, the randomization date will be used instead of the first dosing date of study drug. For screen failures, the date the informed consent was signed will be used for age calculation. If only the birth year is collected on the CRF, "01 July" will be used for the unknown birth day and month for the purpose of age calculation. If only birth year and month are collected, "01" will be used for the unknown birth day.

Non-PK data that are continuous in nature but are less than the lower limit of quantitation (LOQ) or above the upper LOQ will be imputed as follows:

- A value that is 1 unit less than the LOQ will be used to calculate descriptive statistics if the datum is reported in the form of "< x" (where x is considered the LOQ). For example, if the values are reported as < 50 and < 5.0, values of 49 and 4.9, respectively, will be used to calculate summary statistics. An exception to this rule is any value reported as < 1 or < 0.1, etc. For values reported as < 1 or < 0.1, a value of 0.9 or 0.09, respectively, will be used to calculate summary statistics.
- A value that is 1 unit above the LOQ will be used to calculate descriptive statistics if the datum is reported in the form of "> x" (where x is considered the LOQ). Values with decimal points will follow the same logic as above.
- The LOQ will be used to calculate descriptive statistics if the datum is reported in the form of "≤ x" or "≥ x" (where x is considered the LOQ).

Natural logarithm transformation will be used for plasma/blood concentrations and analysis of PK parameters. Plasma concentration values that are below the limit of quantitation (BLQ) will be presented as “BLQ” in the concentration data listing. Values that are BLQ will be treated as 0 at predose time points, and one-half the value of the LOQ at postbaseline time points.

The following conventions will be used for the presentation of summary and order statistics:

- If at least 1 subject has a concentration value of BLQ for the time point, the minimum value will be displayed as “BLQ.”
- If more than 25% of the subjects have a concentration data value of BLQ for a given time point, the minimum and Q1 values will be displayed as “BLQ.”
- If more than 50% of the subjects have a concentration data value of BLQ for a given time point, the minimum, Q1, and median values will be displayed as “BLQ.”
- If more than 75% of the subjects have a concentration data value of BLQ for a given time point, the minimum, Q1, median, and Q3 values will be displayed as “BLQ.”
- If all subjects have concentration data values of BLQ for a given time point, all order statistics (minimum, Q1, median, Q3, and maximum) will be displayed as “BLQ.”

PK parameters that are BLQ will be imputed as one-half LOQ before log transformation or statistical model fitting.

3.8. Analysis Visit Windows

3.8.1. Definition of Study Day

Study day will be calculated from the first dosing date of study drug and derived as follows:

- For postdose study days: Assessment Date – First Dosing Date + 1
- For days prior to the first dose: Assessment Date – First Dosing Date

Therefore, study Day 1 is the day of first dose of study drug administration.

For placebo subjects who were re-randomized to active treatment, the On-Active-Treatment study day will be calculated as: Assessment Date – Date of the first dose of active treatment + 1. The date of the first dose of active treatment is recorded on CRF.

3.8.2. Analysis Visit Windows

The target study days for analysis visits are provided in the [Table 2](#) below:

Table 2. Target Days for Analysis Visits

Nominal Visit	Nominal Study Day/ Study Day on Active Treatment
Screening	< 1
Baseline	<=1
Week 2	15
Week 4	29
Week 8	57
Week 12	85
Week 18	127
Week 24	169/1
Week 26	183/15
Week 28	197/29
Week 32	225/57
Week 36	253/85
Week 42	295/127
Week 48	337/169
Follow-up Visit	NA

The nominal visit as recorded on the CRF will be used when data are summarized by visit.

Any data recorded under unscheduled visits will not be assigned to a particular visit or time point. However, the following exceptions will be made:

- An unscheduled visit prior to the first dosing of study drug may be included in the calculation of the baseline or screening value, if applicable
- Unscheduled visits after the first dose of study drug will be included in determining the maximum postbaseline toxicity grade in safety analyses

For subjects who prematurely discontinue from the study, early termination (ET) data will be assigned to what would have been the next scheduled visit where the respective data were scheduled to be collected. If this next scheduled visit for parameter falls on the visit after the latest performed scheduled visit as reported in the clinical database then the analysis visit is not assigned and the value is not included in the analyses.

Data collected at a follow-up visit will be summarized under a separate visit, and labeled “Follow-up Visit.”

3.8.3. Selection of Data in the Event of Multiple Records in an Analysis Visit Window

Depending on the statistical analysis method, single values may be required for each analysis window.

If multiple valid, nonmissing, continuous measurements exist in an analysis window, records will be chosen based on the following rules if a single value is needed:

- In general, the baseline value will be the last nonmissing value on or prior to the first dosing date of study drug, unless specified differently. If multiple measurements occur on the same day, the last nonmissing value prior to the time of first dosing of study drug will be considered as the baseline value. If these multiple measurements occur at the same time or the time is not available, the average of these measurements will be considered the baseline value.
- For postbaseline values:
 - The record closest to the nominal day for that visit will be selected.
 - If there are 2 records that are equidistant from the nominal day, the later record will be selected.
 - If there is more than 1 record on the selected day, the average will be taken, unless otherwise specified.

If multiple valid, non-missing, categorical measurements exist in an analysis window, records will be chosen based on the following rules if a single value is needed:

- For baseline, the last available record on or prior to the date of the first dose of study drug will be selected. If there are multiple records with the same time or no time recorded on the same day, the value with the lowest severity will be selected (e.g., normal will be selected over abnormal for safety electrocardiogram [ECG] findings).
- For postbaseline visits, if there are multiple records with the same time or no time recorded on the same day, the value with the worst severity within the window will be selected (e.g., abnormal will be selected over normal for safety ECG findings).

All records will be listed by collection date.

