1.2. Study Design

This is a Phase 2, multicenter, randomized, double-blind, placebo-controlled study to evaluate the safety and efficacy of filgotinib, lanraplenib (GS-9876), and tirabrutinib (GS-4059) in adult male and female subjects with active SjS.

At Day 1, eligible subjects will be randomized 1:1:1:1 to daily oral filgotinib (200 mg), lanraplenib (30 mg), tirabrutinib (40 mg) or placebo to match (PTM). Randomization will be stratified by: use of concurrent immunomodulatory drugs at baseline (Y/N: conventional synthetic disease modifying antirheumatic drugs (csDMARD[s]) or corticosteroids), and the hematologic + biological component scores of the EULAR Sjogren's syndrome disease activity index (ESSDAI) obtained at screening (combined score of <2 or ≥ 2).

[figure not shown]
Stable medications at Day 1 should be continued during the study dosing period through Week 48. Dose adjustments for toxicities and dose adjustment of corticosteroids are allowed after Week 12. Subjects will return to the study site for scheduled study visits at Weeks 2, 4, 8, 12, 18, 24, 26, 28, 32, 36, 42, and 48 ([Appendix 1](#)).

At completion of the Week 24 visits, subjects on placebo will be re-randomized 1:1:1, in a blinded fashion, to daily oral filgotinib (200 mg), lanraplenib (30 mg), or tirabrutinib (40 mg) without further stratification. Dosing and assessments for all subjects will continue through Week 48.

CCI

Subjects who discontinue study drug for any reason (other than noncompliance) may continue to participate in scheduled study visits and procedures, as long as deemed medically appropriate by the investigator. Subjects who discontinue all study participation will have an early termination (ET) visit; these subjects, and those who complete the study, should return to the study site for a follow-up visit, 4 weeks after the last dose of study drug (subjects who have discontinued study drug \geq 4 weeks prior to the ET/Week 48 visit, do not need a follow up visit).

Figure 1. Study Design Schematic

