3.9. Efficacy Estimands

Three efficacy estimands: a treatment-policy estimand, a hypothetical estimand and a composite estimand, are defined for the primary and secondary efficacy endpoints.

The **treatment-policy estimand** is the primary estimand for the primary and secondary efficacy endpoints.

1) Population: Subjects in the FAS

- 2) Variable: Primary and secondary endpoints
- 3) Intercurrent events: The occurrence of an intercurrent event is irrelevant. All observed values will be used regardless of occurrence of an intercurrent event

The **hypothetical estimand** is defined as following. This is the supportive estimand for the primary and secondary efficacy endpoints.

- 1) Population: Subjects in the Full Analysis Set (FAS).
- 2) Variable: Primary and secondary endpoints
- 3) Intercurrent events: The following intercurrent events are taken into account:
 - Subject takes prohibited medication
 - Subject changes the dose of the medication required to be stable per protocol
 - Subject discontinues from study treatment

The **composite estimand** is defined as following. This is the supportive estimand for the primary and secondary efficacy endpoints.

- 1) Population: Subjects in the Full Analysis Set (FAS).
- 2) Variable: Primary and secondary endpoints
- 3) Intercurrent events: The following intercurrent events are taken into account:
 - Subject takes prohibited medication
 - Subject changes the dose of the medication required to be stable per protocol
 - Subject discontinues from study treatment

The estimators associated with each of these estimands are described in [Table 3](#) of Section 6.

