Completion of the study up to Week 12 will be based on the presence of the corresponding visit in EDC or presence of Early Termination visit which is after Week 8 visit. Completion of treatment up to Week 12 is considered when the [date of last dose – date of first dose + 1] \geq 82 days (target date for Week 12 visit minus protocol allowed visit window). Similar algorithm is applied to Week 24 completion. Subjects are considered to complete 24 weeks of treatment if the start date of Week 24 treatment is provided or the [last dose date – first dose date + 1] \geq 166. Subjects who complete Week 24 visit/treatment but did not continue beyond Week 24 are reported as “Discontinued at Week 24”.

The by-subject listing of disposition will be provided by subject identification (ID) number in ascending order to support the above summary tables.

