6.3. Analysis for the Primary Efficacy Endpoint

6.3.1. Primary Analysis of Primary Endpoint

In the primary analysis, the primary outcome in each active treatment group will be compared to the outcome in the placebo group using a superiority test at the 2-sided 0.05-level. The following null hypotheses will be tested (vs. the respective alternative hypotheses):

- H01: There is no difference in the responder rate between filgotinib 200 mg group and placebo group at Week 12
- H02: There is no difference in the responder rate between lanraplenib 30 mg group and placebo group at Week 12
- H03: There is no difference in the responder rate between tirabrutinib 40 mg group and placebo group at Week 12

The analyses will be performed using Cochran Mantel Haenszel (CMH) test adjusted for the randomization stratification factors. If CMH test stratified by both stratification factors is not appropriate due to small cell counts then the levels of the stratification by ESSDAI scores will be pooled, and the analysis will be stratified only by use of concurrent immunomodulatory drugs at baseline. Each of the three hypotheses will be tested separately at the 2-sided, 0.05-level.

The primary analysis will be based on the Treatment Policy Estimand, with missing values imputed by multiple imputation method described in Section 6.1.

The number and percentage of responders in each treatment group as well as 95% confidence intervals (CIs) will be presented for each visit.

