12. APPENDIXES

Appendix 1. Schedule of Assessments

	Screening ^a	Day 1 ^b	Week 2	Week 4	Week 8	Week 12	Week 18	Week 24	Week 26	Week 28	Week 32	Week 36	Week 42	Week 48/ET ^c	Follow Up visit 4 weeks after subject's last study visit ^d
Visit window	None	None	+/- 3 days	+/- 3 days	+/- 3 days	+/- 3 days	+/- 3 days	+/- 3 days	+/- 3 days	+/- 3 days	+/- 3 days	+/- 7 days	+/- 7 days	+/- 7 days	+/- 7 days
Fasting visit		x				X		x						x	
IP to be taken at the clinic		x	x	x	x	X	x	x	x	x	x	x	x	x	
Written Informed Consent	x														
Randomization		x ^e						x ^f							
Physical exam and provider assessments															
SjS medical/surgical history, including diagnosis and prior treatments,	x														
Medical /Surgical History (non-SjS)	x														
Vital Signs, including weight and height ^g	x	x	x	x	x	X	x	x	x	x	x	x	x	x	x
Complete Physical Examination	x							x						x	
Symptom-directed PE		x	x	x	x	X	x		x	x	x	x	x		x
ESSDAI	x	x ^y		x	x	X	x	x		x	x	x	x	x	
PE for domains of ESSDAI ^h	x	x		x	x	X	x	x		x	x	x	x	x	
28 Swollen and Tender Joint count	x	x	x	x	x	X	x	x	x	x	x	x	x	x	

	Screening ^a	Day 1 ^b	Week 2	Week 4	Week 8	Week 12	Week 18	Week 24	Week 26	Week 28	Week 32	Week 36	Week 42	Week 48/ET ^c	Follow Up visit 4 weeks after subject's last study visit ^d
Visit window	None	None	+/- 3 days	+/- 3 days	+/- 3 days	+/- 3 days	+/- 3 days	+/- 3 days	+/- 3 days	+/- 3 days	+/- 3 days	+/- 7 days	+/- 7 days	+/- 7 days	+/- 7 days
Physician's Global Assessment of SjS activity	x	x	x	x	x	X	x	x	x	x	x	x	x	x	x
Physician's Global Assessment of concomitant RA or SLE disease activity as applicable	x	x	x	x	x	X	x	x	x	x	x	x	x	x	x
Laboratory assessments															
Urine drug screen ⁱ	x														
Urinalysis with spot protein/microalbumin/creatinine	x	x	x	x	x	X	x	x	x	x	x	x	x	x	
Urine Pregnancy Test (female subjects of child bearing potential only)		x	x	x	x	X	x	x	x	x	x	x	x	x	x
Urine for biomarker (fasting)		x				X		x						x	
Serum Pregnancy Test (female subjects of child bearing potential) or FSH	x														
TB testing ^j	x														
CD19+ B cell count ^k	x														
HbA1c, TSH	x														
Hematology, ESR as applicable, chemistry and hsCRP	x	x	x	x	x	X	x	x	x	x	x	x	x	x	x
Viral Screening and Reflex PCR ^l	x														
Viral Monitoring ^m						X		x				x		x	

[figure not shown]
	Screening ^a	Day 1 ^b	Week 2	Week 4	Week 8	Week 12	Week 18	Week 24	Week 26	Week 28	Week 32	Week 36	Week 42	Week 48/ET ^c	Follow Up visit 4 weeks after subject's last study visit ^d

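### The two early-termination sentences in SAP 3.8.2 contradict each other, so an in-window ET assessment after Week 8 does not count as Week 12 and the response is imputed

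*SAP*

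**What the plan says.** SAP 3.8.2 contains two consecutive rules for subjects who leave the study early. First, their ET data "will be assigned to what would have been the next scheduled visit where the respective data were scheduled to be collected". Second, if that next visit "falls on the visit after the latest performed scheduled visit as reported in the clinical database then the analysis visit is not assigned". Such a value then drops out of the analyses. Otherwise visits are assigned by CRF label: "The nominal visit as recorded on the CRF will be used when data are summarized by visit". Table 2 of the SAP lists target days only, with no day ranges.

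These SAP sections bear on the rule:

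- **1.2** says who has such a record: "Subjects who discontinue all study participation will have an early termination (ET) visit".
- **Appendix 1** marks the row "Hematology, ESR as applicable, chemistry and hsCRP" and the VAS and ESSPRI rows at every visit, including the Week 48/ET column. ESSDAI is marked at all of them except Weeks 2 and 26 (and follow-up).
- **3.9** defines the primary, treatment-policy estimand: "All observed values will be used regardless of occurrence of an intercurrent event".
- **4.1** counts a subject as completing the study up to Week 12 on the Week 12 visit itself or on the "presence of Early Termination visit which is after Week 8 visit". A similar rule applies at Week 24.
- **6.3.1** runs the primary analysis "with missing values imputed by multiple imputation method described in Section 6.1". Appendix 2 makes the response missing when a post-baseline VAS is missing.

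**The concern.** The second ET sentence removes exactly the assignment that the first one makes. A subject can attend inside the protocol's Week 12 window, give all five VAS and an hsCRP sample, leave the study that day, and still have no Week 12 response if the attendance is filed as ET. The value is then multiply imputed from a binary model whose only named covariates are the stratification factors (SAP 6.1). Under the composite estimand it becomes a non-response (SAP Table 3). In the disposition table the same attendance counts as Week 12 completion.

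This rule decides which primary-endpoint data count. As written, one programmer could follow the first sentence and another the second, and their Week 12 datasets would differ. A choice made after the Week 24 results are unblinded could look data-driven.

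**Working it through.** **1. Windows.** Inputs: target Day 85 for Week 12 and Day 169 for Week 24 (SAP Table 2), each ±3 days (SAP Appendix 1).
- Week 12: 85 − 3 = 82 and 85 + 3 = 88, so Day 82-88.
- Week 24: 169 − 3 = 166 and 169 + 3 = 172, so Day 166-172.
- The lower limits reproduce the SAP's own treatment-completion thresholds in 4.1 (at least 82 and at least 166 days).

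**2. The rule applied literally.** Take each possible last performed visit from Day 1 to Week 42 (12 cases), with no visit skipped and the next visit counted from the last one performed. Read the visit after as the immediately following visit.

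| Parameter | ET value kept | ET value dropped |
|---|---|---|
| VAS, hsCRP, ESSPRI | 0 of 12 | 12 of 12 |
| ESSDAI | 2 of 12 (Day 1 to Week 4; Week 24 to Week 28) | 10 of 12, including Week 8 to Week 12 and Week 18 to Week 24 |

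The two ESSDAI cases kept are those where the target visit is two visits away, so near values are dropped and far ones kept. If the visit after means any later visit, everything is dropped.

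**3. The other way to count.** Suppose the next scheduled visit is counted from the ET date, and the last performed visit is Week 8.
- ET on Day 82-84: the next visit is Week 12, which directly follows Week 8, so the value is dropped.
- ET on Day 86-88: the next visit is Week 18. On the immediately-following reading the value is kept, but as Week 18. On the any-later reading it is dropped.
- ET on Day 85: one or the other, depending on how a tie is treated.

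On none of these readings does this subject's in-window ET value count as Week 12.

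**4. Size.** The documents give no dropout rate. Assume 5-15% leave at an even daily rate over the 84 days before Week 12, that the same daily rate continues afterwards, and that every such attendance is entered as ET. Expected number per arm = 35 × rate × days/84.

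| Period | Days | Per arm at 5% | Per arm at 15% |
|---|---|---|---|
| Day 82-88 (Week 12 window) | 7 | 0.146 | 0.438 |
| Day 166-172 (Week 24 window) | 7 | 0.146 | 0.438 |
| Day 58-84 (from the day after the Week 8 target) | 27 | 0.563 | 1.688 |
| Day 128-168 (from the day after the Week 18 target) | 41 | 0.854 | 2.563 |

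Over four arms, Day 82-88 gives 4 × 0.146 = 0.58 to 4 × 0.438 = 1.75 subjects. If every one of those imputed responses were wrong, an arm's responder rate would move by 0.146/35 = 0.4 to 0.438/35 = 1.3 percentage points. A single affected subject is worth at most 1/35 = 2.9 points.

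**The case against.** The strongest reply is that the case is narrow. It needs a subject who attends in the window, leaves the study, and has the attendance filed as ET rather than as Week 12; a record labelled Week 12 is kept. Subjects who only stop study drug may stay on scheduled visits and are not touched. In a proof-of-concept trial, less than one expected subject per arm is a small matter. All of this stands, and it limits the severity.

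A reader might go further and infer that every ET value after Week 8, from Day 58 on, is an observed Week 12 result discarded against 3.9. The documents do not support that. A Day 58-81 value lies outside the protocol's window, and leaving it unassigned is compatible with treatment policy. Section 3.9 concerns values observed despite intercurrent events; those the SAP names are prohibited medication, changes to stable medication and stopping study treatment, not leaving the study. The conflict with 3.9 is clear only inside the window.

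A reader might also infer that the value is lost on every reading. It is not: counted from the ET date, a Day 86-88 value can land at Week 18. That changes where the value goes, but Week 12 is still empty.

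Finally, the second sentence may have been meant to exclude ET values whose next collection visit lies beyond the immediately following one. Section 4.1 points that way. This supports correcting the sentence, since the text says something else.

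**Conclusion.** The contradiction is real and should be corrected. For a subject who skipped no visit, the second ET sentence cancels the first for all components of the primary endpoint and for ESSPRI, and for ESSDAI at both secondary time points, when the next visit is counted from the last one performed. Counting from the ET date changes the route but does not restore an in-window value to Week 12 for a subject last seen at Week 8.

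The clear harm is confined to ET attendances inside Day 82-88, or Day 166-172 for Week 24, that are not entered as the nominal visit. That is about 0.15-0.44 subjects per arm for each time point, under the assumed 5-15% dropout at an even rate. The effect on ESSDAI and ESSPRI is milder, because their imputation model also uses the baseline value and the repeated-measures model uses earlier visits. Nothing here suggests a material bias in the trial's result. The reason to act is that the rule governs primary-endpoint data, contradicts itself and 4.1, and can be settled while the treatment results are still blinded.

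**What to change.** Before the Week 24 unblinding, replace both ET sentences in SAP 3.8.2 with:

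> ET data collected within the protocol window of a scheduled visit at which the parameter is due are assigned to that visit if it has no record. Other ET data are assigned to the scheduled visit immediately following the latest performed one if the parameter is due there; otherwise they have no analysis visit and are left out of by-visit analyses.

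The first part settles the in-window case without relying on how the next visit is counted. It also covers a subject who missed Week 8 and has an ET on Day 82-88. The second part keeps VAS, hsCRP and ESSPRI in 12 of 12 cases and ESSDAI in 10 of 12, including Week 8 to Week 12 and Week 18 to Week 24. The two ESSDAI cases it leaves out (last visit Day 1 or Week 24) do not feed the Week 12 or Week 24 endpoints.

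The cost is one short paragraph in the SAP and a change to the visit-mapping code. The downside is that the second part, like the SAP's own first sentence and 4.1, lets an ET value from Day 58 stand as Week 12 (85 − 58 = 27 days early) and one from Day 128 stand as Week 24 (169 − 128 = 41 days early). At the assumed dropout rates, more subjects fall in those spans than in the windows themselves. If the sponsor prefers a study-day limit, the same limit should be used in 3.8.2 and 4.1.
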